1.3.3 Guadecitabine Clinical Data

For the most updated clinical data, please refer to the most recent Investigator Brochure.

Guadecitabine was studied in a first-in-human, single-agent study (SGI-110-01). This study was a Phase 1/2, dose escalation, multicenter study of two subcutaneous regimens of guadecitabine in subjects with intermediate or high-risk myelodysplastic syndromes (MDS) or acute myeloid leukemia (AML). This study had two parts: a Dose Escalation Segment and a Dose Expansion Segment. The study sought to evaluate the biological activity, preliminary safety, and efficacy of guadecitabine with two dosing schedules in intermediate to high risk MDS or relapsed or refractory AML subjects, while the Dose Expansion Segment further evaluated the safety and efficacy at the recommended dose. The study was based on a 3 + 3 design within each regimen. The recommended dose going forward was 60mg/m² QD x 5 days, every cycle being 28 days ²².

Guadecitabine was also studied in a phase I leading into a randomized phase II study in combination with Carboplatin in patients with recurrent ovarian cancer (Study SGI-110-02). Two dose levels of guadecitabine were studied: 30mg/m² QD x 5 days with Carboplatin AUC 4 and 45mg/m² qd X 5 days with Carboplatin AUC 5. The second dose level was not tolerated, with neutropenic fever and thrombocytopenia being DLTs. The dose taken for further development in the randomized phase II portion of the trial was 30mg/m² QD x 5 days with Carboplatin AUC, each cycle being 28 days ¹⁷.

1.3.4 Clinical Efficacy/Biological Activity/Safety of Guadecitabine

Based on PD assessment of global hypomethylation from the first 7 cohorts in Study SGI-110-01, the LINE-1 demethylation data show dose dependent hypomethylation induction in the daily schedule reaching a plateau at cohort 5 (60 mg/m²). The Biologically Effective Dose or BED, therefore, was established as 60 mg/m² SC daily x 5. The hypomethylation of the weekly schedule was inferior to the daily schedule and plateaued early (daily x 5) ²². In the ovarian cancer SGI-110-02 study, LINE-1 methylation was measured at both dose levels (Figure 4). Effective LINE-1 hypomethylation (~17%) was observed and was similar at both dose levels ¹⁷. Therefore, in this

NU Study Number: NU 16G03
Merck Study Number: 3475-244

protocol, we will use the lower dose of 30mg/m², which has been shown to induce hypomethylation and gene re-expression.

Of note is that the current protocol will use a shorter cycle duration (21 days, as compared to 28 days in previous studies). We will use the 21 day course to accommodate a regimen giving pembrolizumab q 3 weeks. We anticipate that the shorter course will be tolerated, given that 30mg/m² daily for 5 days given in combination with Carboplatin was tolerated.

SGI-110 Cohort (mg/m ² qd x5)	Max LINE-1 Demethylation
1 (45)	-17.4 ± 6.9% (n=6)
2 (30)	-19.5 ± 8.6 % (n=14)

[figure not shown]

Figure 4 LINE-1 Demethylation in Blood DNA B) Individual Patients Max LINE-1 Demethylation

[figure not shown]
1.4 Rationale for the Current Study

We speculate that an important mechanism of immune evasion in OC is represented by epigenetic silencing of tumor antigens. We and others have shown that OC progression is accompanied by the establishment of stable and transcriptionally repressive epigenetic modifications^{10, 11}. Some of these modifications include DNA methylation at promoters of genes encoding tumor antigens that serve as potent immunogenic stimuli in the anti-tumor response. DNA methylation is regulated by DNA methyl transferases (DNMT-1, -3a and -3b). Recent studies have shown that DNMT inhibitors (DNMTI) cause DNA hypomethylation and restore the expression of epigenetically silenced genes, including tumor suppressor genes¹² and tumor antigens. DNMTIs have become therapeutically relevant in hematologic cancers^{13,14} and are being explored in solid tumors in combination with chemotherapy¹⁵. **Here we hypothesize that the use of a novel DNMTI (guadecitabine) will reverse**

NU Study Number: NU 16G03
Merck Study Number: 3475-244

silencing of tumor antigens, restore their expression, and potentiate the effects of immune interventions.

Our preliminary data support that treatment with guadecitabine *in vitro* causes significant up-regulation of tumor antigens including *Muc16* (encoding CA-125), *Mage A2*, *Mage A11*, and *cancer testis antigen (NY-ESO 1)* in OC cell lines (Fig. 1). We speculate that these effects render OC cells more recognizable by the immune system *in vivo*. Furthermore, analyses of tumor material obtained from another ongoing clinical trial using guadecitabine in combination with carboplatin in women with OC¹⁷ showed significant treatment-induced hypomethylation of *Mage A2* and *Mage A11* (as measured by DNA pyrosequencing, Fig. 2A) in tumor biopsies obtained after 2 cycles of guadecitabine compared to baseline biopsies. Re-expression of the tumor antigens *NY-ESO-1* and *MAGE A3* was confirmed by RT-PCR in tumor biopsies obtained after 2 cycles of guadecitabine compared to baseline (Fig. 2), demonstrating that hypomethylating agents induce tumor antigen re-expression in human tumors, by reducing DNA methylation. These data support a strategy combining epigenome editing using guadecitabine along with immunomodulatory approaches, as proposed here. Based on the recent knowledge that the anti-PD1 antibody pembrolizumab (P) has impressive clinical activity in solid tumors^{18,19}, and is well tolerated and induces durable responses in patients with advanced epithelial ovarian cancer, we propose to use PD-1 blockade (P) in combination with guadecitabine in preclinical and clinical OC models.

1.4.1 Rationale for Dose Selection/Regimen/Modification

An open-label Phase I trial (Protocol 001) evaluated the safety and clinical activity of single agent MK-3475. The dose escalation portion of this trial evaluated three dose levels, 1 mg/kg, 3 mg/kg, and 10 mg/kg, administered every 2 weeks (Q2W) in subjects with advanced solid tumors. All three dose levels were well tolerated and no dose-limiting toxicities were observed. This first in human study of MK-3475 showed evidence of target engagement and objective evidence of tumor size reduction at all dose levels (1 mg/kg, 3 mg/kg and 10 mg/kg Q2W). No MTD has been identified to date. 10.0 mg/kg Q2W, the highest dose tested in PN001, will be the dose and schedule utilized in this protocol to test for initial tumor activity. Recent data from other clinical studies within the MK-3475 program has shown that a lower dose of MK-3475 and a less frequent schedule may be sufficient for target engagement and clinical activity.

PK data analysis of MK-3475 administered Q2W and Q3W showed slow systemic clearance, limited volume of distribution, and a long half-life (refer to

NU Study Number: NU 16G03
Merck Study Number: 3475-244

IB). Pharmacodynamic data (IL-2 release assay) suggested that peripheral target engagement is durable (>21 days). This early PK and pharmacodynamic data provides scientific rationale for testing a Q2W and Q3W dosing schedule.

A population pharmacokinetic analysis has been performed using serum concentration time data from 476 patients. Within the resulting population PK model, clearance and volume parameters of MK-3475 were found to be dependent on body weight. The relationship between clearance and body weight, with an allometric exponent of 0.59, is within the range observed for other antibodies and would support both body weight normalized dosing or a fixed dose across all body weights. MK-3475 has been found to have a wide therapeutic range based on the melanoma indication. The differences in exposure for a 200 mg fixed dose regimen relative to a 2 mg/kg Q3W body weight based regimen are anticipated to remain well within the established exposure margins of 0.5 – 5.0 for MK-3475 in the melanoma indication. The exposure margins are based on the notion of similar efficacy and safety in melanoma at 10 mg/kg Q3W vs. the proposed dose regimen of 2 mg/kg Q3W (i.e. 5-fold higher dose and exposure). The population PK evaluation revealed that there was no significant impact of tumor burden on exposure. In addition, exposure was similar between the NSCLC and melanoma indications. Therefore, there are no anticipated changes in exposure between different indication settings.

The rationale for further exploration of 2 mg/kg and comparable doses of pembrolizumab in solid tumors is based on: 1) similar efficacy and safety of pembrolizumab when dosed at either 2 mg/kg or 10 mg/kg Q3W in melanoma patients, 2) the flat exposure-response relationships of pembrolizumab for both efficacy and safety in the dose ranges of 2 mg/kg Q3W to 10 mg/kg Q3W, 3) the lack of effect of tumor burden or indication on distribution behavior of pembrolizumab (as assessed by the population PK model) and 4) the assumption that the dynamics of pembrolizumab target engagement will not vary meaningfully with tumor type.

The choice of the 200 mg Q3W as an appropriate dose for the switch to fixed dosing is based on simulations performed using the population PK model of pembrolizumab showing that the fixed dose of 200 mg every 3 weeks will provide exposures that 1) are optimally consistent with those obtained with the 2 mg/kg dose every 3 weeks, 2) will maintain individual patient exposures in the exposure range established in melanoma as associated with maximal efficacy response and 3) will maintain individual patients exposure in the exposure range established in melanoma that are well tolerated and safe.

A fixed dose regimen will simplify the dosing regimen to be more convenient for physicians and to reduce potential for dosing errors. A fixed dosing scheme will also reduce complexity in the logistical chain at treatment facilities and reduce wastage.

To match the required q 3 weeks administration of pembrolizumab, the cycle of guadecitabine has been modified from D1-5 every 4 weeks (as previously administered in Study SGI-110-02) to a regimen using D1-4 every 3 weeks. This modification allows the administration of similar doses of guadecitabine over time (e.g. 480mg/m² in 12 weeks with the 3 weekly regimen compared to 450mg/m² in 12 weeks with the 4 weekly regimen). The D1-4 guadecitabine regimen every 3 weeks has been found to be tolerable in a

NU Study Number: NU 16G03
Merck Study Number: 3475-244

cholangiocarcinoma study (personal communication from Astex, unpublished).

1.4.2 Safety run-in cohort

As stated earlier, this study proposes to use the combination of pembrolizumab with guadecitabine in subjects with ovarian cancer. The combination of pembrolizumab with guadecitabine has not been previously tested in this subject population. Hence, a safety run-in cohort has been designed for the first six subjects enrolled, in order to ensure the safety of this combination of agents. Refer to section 4.3 for details on how this will be conducted.

1.5 Exploratory Studies

To test the hypothesis that the combination of guadecitabine and pembrolizumab reactivates immune responses by allowing re-expression of tumor antigens silenced epigenetically, we will measure several exploratory endpoints. All biological parameters will be correlated with clinical endpoints (ORR, CBR, and PFS).

- NY-ESO-1 and *MAGE* antigens' promoter methylation (pyrosequencing) and mRNA expression levels (quantitative RT-PCR) will be measured before and after treatment in DNA (plasma and tumor biopsies) and RNA (tumor biopsies), respectively.
- Cytokine response (IFN γ , IL2, IL6, IL10, TNF α) will be measured in plasma by ELISA.
- Expression of the PD-L1 ligand will be measured by IHC in archival tumors.
- Measure LINE 1 methylation in DNA extracted from PBMCs (D5 vs. D1 of cycles 1 and 2).
- Tumor infiltrating lymphocytes (TILs) will be quantified in tumor biopsies before and after treatment (IHC), including in optional samples collected > 6 months on treatment.

2.0 OBJECTIVES & ENDPOINTS

2.1 Primary Objective & Endpoint

Measure objective response rate (ORR) to guadecitabine and pembrolizumab in subjects with recurrent platinum resistant Ovarian Cancer (OC) using RECIST v1.1. The objective response rate as defined by RECIST v1.1 is the proportion of all subjects with confirmed PR or CR according to RECIST v1.1, from the start of treatment until disease progression/recurrence (taking as reference for progressive disease the smallest measurements recorded since the start of treatment).

2.2 Secondary Objectives & Endpoints

2.2.1 Measure progression free survival (PFS) for the combination of guadecitabine and pembrolizumab.

Progression free survival (PFS) is defined per RECIST v1.1 as the time from the date of registration until the criteria for disease progression is met as defined by RECIST 1.1 or death occurs.

2.2.2 Measure clinical benefit rate (CBR) for the combination of guadecitabine and pembrolizumab.

(Note: CBR is defined as Objective Response Rate (CR + PR) plus Stable Disease for at least 3 months)

2.2.3 Measure toxicity profiles to the combination of guadecitabine and pembrolizumab.

2.2.4 Measure objective response rate (ORR) to the combination of guadecitabine and pembrolizumab using the Immune Related Response Criteria (irRC) (*Note: Response assessments will be made using both irRC and RECIST v1.1, allowing additional comparisons among these criteria for disease response assessment. Measurable and non-measurable lesions will be followed by both RECIST v1.1 & irRC. Disease progression will be determined using RECIST 1.1 criteria. (Refer to section 6.0 for details.)*)

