Statistical Methodology	
This is a non-randomized, open label phase II study. Study endpoints are defined in Section 6.0
 
We will utilize the optimum two stage design, and we anticipate enrolling 35 evaluable patients. This two-stage design, which will test the null hypothesis that ORR<=0.10 versus the alternative that ORR>=0.30 (where ORR is calculated via RECIST v1.1), has an expected sample size of 22.5 and a probability of early termination of 0.71 when ORR=0.10. If the drug combination is actually not effective, there is a 0.047 probability of concluding that it is (the target for this value was 0.050). If the drug is actually effective, there is a 0.098 probability of concluding that it is not (the target for this value was 0.100). After testing the drug on 18 patients in the first stage, consideration will be given to trial termination if 2 or fewer patients demonstrate clinical benefit (CR, PR, or SD for at least 3 months). If the trial goes on to the second stage, a total of 35 evaluable patients will be studied. If the total number responding is less than or equal to 6, the combination is rejected. Subjects who are not evaluable for response will be replaced so that up to 46 subjects will be enrolled.

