4.0 TREATMENT PLAN

4.1 Overview

All subjects will be treated in cycles lasting 21 days (3 weeks). The drugs being used in this study include pembrolizumab and guadecitabine. Guadecitabine 30mg/m² will be administered as a subcutaneous injection on Days 1-4 of every 21 day cycle. Pembrolizumab 200 mg will be administered as a 30 minute IV infusion on Day 5 of every 21 day cycle. ***Patients must begin therapy within (+) 14 days of registration.***

For patients on combination therapy, treatment should be initiated on Day 1 of each cycle. NOTE: For patients receiving the combination of guadecitabine and pembrolizumab, guadecitabine dosing on Day 1 of each cycle should always begin on a Monday in order for the patient to receive pembrolizumab on Friday (Day 5). In the event of holidays or scheduling difficulties for administrative reasons, Day 1 of each cycle may be delayed up to +28 days. All treatments will be administered on an outpatient basis. Treatment will continue until disease progression, unacceptable toxicity, patient withdrawal, or death. NOTE: please see section 4.4.1 for conditions under which patients may be permitted to continue on single agent pembrolizumab only. One dose of guadecitabine may be skipped during a cycle due to scheduling constraints with holidays (e.g. if Memorial Day is on a weekday, the patient may skip that dose of guadecitabine). The decision to skip a dose of guadecitabine vs dose delay will be at the discretion of the treating physician.

Please refer to Section 5.2 (table) for treatment details regarding patients on Pembrolizumab monotherapy.

To exclude prohibitive toxicity, a safety run-in cohort of the initial 6 patients will be done. All subjects in the run-in cohort will be observed for at least 2 weeks after completion of cycle 1 for dose limiting toxicity (DLT) (Refer section 4.3)

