6.3 Secondary Endpoints

Measure progression free survival (PFS) and clinical benefit rate (CBR) to the combination of guadecitabine and pembrolizumab.

PFS will be defined as the time from first dose of study treatment until disease progression or death from any cause. Any patient who has completed at **least 1 cycle of treatment** will be evaluable for PFS endpoint.

Clinical Benefit Rate(CBR) will be defined as patients with CR + PR or SD (SD for at least 3 months). Any patient who has completed at **least 2 cycles of treatment** will be evaluable for CBR endpoint.

Measure toxicity profiles for the combination of guadecitabine and pembrolizumab. The number, type, grade, severity, and frequency of adverse events will be tabulated; adverse events are assessed at least once per cycle. Any patient who receives **at least one dose** of study therapy will be evaluable for toxicity endpoints.

Measure objective response rate (ORR) to the combination of guadecitabine and pembrolizumab using the Immune Related Response Criteria (irRC)
(Note: Response assessments will be made both using the irRC, and using RECIST v1.1, allowing additional comparisons among these criteria for disease response assessment. Measurable and non-measurable lesions will be followed by both RECIST v1.1 & irRC. Disease progression will be determined using RECIST 1.1 criteria).

6.4 Exploratory Objectives:

To test the hypothesis that the combination of guadecitabine and pembrolizumab reactivates immune responses by allowing re-expression of tumor antigens silenced epigenetically, we will measure several endpoints:

- NY-ESO-1 and MAGE antigens' promoter methylation (pyrosequencing) and mRNA expression levels (quantitative RT-PCR) will be measured before and after treatment in *DNA (plasma and/or tumor biopsies)* and *RNA (tumor biopsies)*, respectively.
- Cytokine response (IFN γ , IL2, IL6, IL10, TNF α) will be measured in plasma by ELISA.
- Measure LINE 1 methylation in DNA extracted from PBMCs (D5 vs. D1 of cycles

NU Study Number: NU 16G03
Merck Study Number: 3475-244

1 and 2).

- Expression of the PD-L1 ligand will be measured by IHC in archival tumors.
- Tumor infiltrating lymphocytes (TILs) will be quantified in tumor biopsies before and after treatment (IHC).

All biological parameters will be correlated with clinical endpoints (ORR and PFS).

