10.1 Study Design

This is a multi-center non-randomized, open label phase II study. Study endpoints are defined in Section 2.0. A safety run-in cohort has been designed for the first six subjects enrolled, in order to ensure the safety of this experimental combination of

NU Study Number: NU 16G03
Merck Study Number: 3475-244

guadecitabine and pembrolizumab.

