10.3.2 Analysis Plans for Secondary Objectives

Confidence intervals for the clinical benefit rate will be calculated similarly to RR. Progression-free survival times will be estimated using the Kaplan-Meier method. The objective response rate by irRC will be estimated similarly. Confidence intervals on the median will be constructed. Toxicities will be tabulated.

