Study summary and Section 10 Statistical considerations. (Sample size and statistics)	Maximum accrual was stated to be 38 in order to obtain 35 evaluable patients. (with an anticipated 1-3 patients that may be inevaluable).	Maximum accrual has been increased to 46 in order to obtain 35 evaluable patients. [This has been done after DSMC approved that 8 more patients can be added to reach 35 evaluable. This request to DSMC was based on the fact there were 5 patients who were enrolled and didn't start study treatment. There were another 7 patients who registered and only had one cycle of treatment, which meant that they were not evaluable for the primary end point. This is a total of 12 patients, when it was initially anticipated that only 1-3 patients would not be evaluable for response. Thus, it became essential to update the total enrollment to 46 in the hope that we will obtain 35 evaluable, with a drop out of 13-14 patients].	Based on the initial DSMC approval that this study can add up to 8 more patients to obtain a total of 35 evaluable patients.
Section 8.1 Drug Section: Pembrolizumab	Previous specifications regarding drug preparation.	Updated with most current specifications for drug preparation	Based on current IB and pharmacy manual.
Section 8.2 Drug section Guadecitabine	Previous specifications regarding drug preparation. and storage	Updated with most current specifications. [Astex sent notification that the current stock of 3ml diluent will be depleted by July 2019 and they will start supplying 1.2ml diluent around this timeframe. So, all documents need to be updated to reflect this.]	Based on updated pharmacy manual from Astex.

NU Study Number: NU 16G03
Merck Study Number: 3475-244

Section 11.9 Publication policy	Previous template language	Updated with most current template language for publication policy	Administrative.
------------------------------------	----------------------------	--------------------------------------------------------------------	------------------------

Protocol Amendment 10 – Version date: October 15, 2020			
Section	Prior Version	Changes in Amendment 10	Rationale
Cover page and throughout	Protocol amendment: 9 Protocol date: January 23, 2019	Protocol amendment: 10 Protocol date: October 15, 2020	Administrative update

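### PFS starts at registration in Section 2.2.1 but at first dose in Section 6.3, and the completed-cycle condition in 6.3 can remove early events

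*Combined protocol and SAP*

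**What the plan says.** Two sections define PFS.

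- Section 2.2.1: "the time from the date of registration until the criteria for disease progression is met as defined by RECIST 1.1 or death occurs". It states no analysis population.
- Section 6.3: "PFS will be defined as the time from first dose of study treatment until disease progression or death from any cause". It adds a population: "Any patient who has completed at least 1 cycle of treatment will be evaluable for PFS endpoint".

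Two cross-references could decide between them, and they disagree. The Statistical Methodology row of the Study Summary states "Study endpoints are defined in Section 6.0"; Section 10.1 states "Study endpoints are defined in Section 2.0".

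The analysis text in Section 10.3.2 reads "Progression-free survival times will be estimated using the Kaplan-Meier method" and adds confidence intervals on the median. It gives no time origin, population or censoring rule.

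On timing, Section 4.1 says "Patients must begin therapy within (+) 14 days of registration", sets 21-day cycles and places all dosing on Days 1 to 5. Footnote 4 of the Section 5.1 schedule puts the first on-treatment scan before Cycle 3. For toxicity, Sections 4.4 and 6.3 require only one dose.

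**The concern.** There are two separate defects.

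The first is the origin. Two analysts who each follow the current text could start the PFS clock on different days, and the plan does not say which of them is right.

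The second lies within Section 6.3. With time running from first dose and death from any cause an event, a patient is at risk from the first injection. The completed-cycle condition then removes a treated patient whose event comes before the end of cycle 1. Whether a patient is counted therefore depends on early outcome, and the patients removed are those who did worst.

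At stake are the reported PFS curve and median, and the exploratory log-rank analyses of biomarkers against PFS in Section 10.3.3.

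**Working it through.** The plan states no PFS median, event count, power or hypothesis, so there is no PFS figure to reproduce. The check is a comparison of text followed by a small calculation.

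**Comparison**

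| Item | Section 2.2.1 | Section 6.3 | Section 10.3.2 |
|---|---|---|---|
| Origin | registration | first dose | not stated |
| Event | RECIST 1.1 progression or death | progression or death from any cause | not stated |
| Population | not stated | at least 1 completed cycle | not stated |
| Censoring | not stated | not stated | not stated |
| Pointed to by | Section 10.1 | Study Summary | neither |

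**Origin.** The largest planned gap from registration to first dose is 14 days (Section 4.1), and 14 / 30.4375 = 0.46 months. The origins therefore differ by 0 to 0.46 months per patient. Registration gives the longer time.

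**Completed-cycle condition.** Suppose n patients are treated, k of them have an event before completing cycle 1, and nobody is censored by then. The Kaplan-Meier curve for all treated patients carries the factor (n − k)/n from those k events, and every later factor is the same with or without them. At any later time t, whatever the shape of the curve:

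S_evaluable(t) = S_all(t) × n / (n − k)

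Inputs:

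- Maximum accrual is 46 (Section 3.0).
- Five patients were enrolled but never started treatment. This is a count reported in the Amendment 9 entry of Appendix V: "This request to DSMC was based on the fact there were 5 patients who were enrolled" and did not begin therapy.
- n = 46 − 5 = 41. This assumes full accrual and no further untreated patients.
- k is not given in the documents; values of 1, 2 and 4 are illustrations.

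Results for a true PFS of 50%:

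- k = 1: 41/40 = 1.025, reported as 51.3%
- k = 2: 41/39 = 1.051, reported as 52.6%
- k = 4: 41/37 = 1.108, reported as 55.4%

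**What limits k.** The protocol does not define completing a cycle for this purpose. If it means that the Day 1 to 5 doses were given, only events in about the first five days are lost. If it means the full 21 days, more can be lost. With no scan scheduled until before Cycle 3, the lost events would be mainly deaths. Patients who stop in cycle 1 without an event also leave the Section 6.3 set; the direction of that effect is unknown and it is not in the calculation.

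**The case against.** The best defence is that this is mostly wording. PFS is secondary, with no test or threshold; the origins differ by two weeks at most; patients enter with ECOG 0 or 1; and no documented patient is shown to have been lost through the condition. All of that stands and limits the size. It does not say which origin applies, and it does not justify selecting patients on early outcome.

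A reader might infer more than the documents support:

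- *That the seven one-cycle patients in the Amendment 9 entry drop out of PFS.* The entry says they had only one cycle and were not evaluable for the primary endpoint, which needs two. They may have completed cycle 1 and so be evaluable for PFS.
- *That Section 2.2.1 puts the five never-treated patients into the PFS analysis.* This is inference from silence. The only stated PFS population, in Section 6.3, excludes them, and Section 4.11 allows their replacement. The five were also counted partway through accrual, so they are not a final share.
- *That one definition gives a longer PFS than the other overall.* Registration lengthens each patient's time, while the completed-cycle condition raises the Section 6.3 curve. The net sign is not established.
- *That 35 can serve as the number treated.* It is the target for response evaluability, which requires two completed cycles. If 35 treated patients met it, k would be zero.

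**Conclusion.** The point holds. The origin conflict is certain from current text, is worth 0 to 14 days per patient, and is left open by opposing cross-references. The completed-cycle condition is wrong in principle. Compared with all treated patients, dropping such events can only raise PFS after cycle 1.

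The size of that bias is conditional. It rests on an unknown k, which may be zero; on an undefined notion of a completed cycle; and, for the illustration, on 41 treated patients with no censoring in cycle 1. Under those assumptions a true 50% is overstated by 1.3 to 5.4 percentage points for one to four lost events. No shift in the median is claimed, because that would need an assumed curve shape.

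The consequences stop at PFS and the exploratory log-rank analyses. The response-rate decision rule is unaffected. The plan should be corrected, but the trial's main conclusion does not depend on it.

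**What to change.** Use one PFS definition in Sections 2.2.1, 6.3 and 10.3.2:

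- Origin: first dose of study treatment.
- Population: all patients who received at least one dose, which is the set already used for toxicity. Delete the completed-cycle condition.
- Event: RECIST 1.1 progression or death from any cause.
- Censoring: patients without an event at their last adequate tumour assessment, or at first dose if they have no post-baseline scan. A death in a patient without such a scan still counts as an event.
- Cross-references: the Study Summary and Section 10.1 should name the same section.

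Registration as origin with all registered patients would also remove the conflict. What matters is one origin and no exclusion based on early outcome.

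The cost is a text amendment with the approvals in Section 11.2, and PFS may come out slightly less favourable. One related inconsistency must be settled with it. Section 4.4.1 takes a patient who cannot complete two combination cycles off the study, while Section 4.9 provides imaging every 9 weeks for those who stop treatment for reasons other than progression. The two passages must be reconciled so that follow-up of these early patients is clear; until then it cannot be assumed that the change needs no extra follow-up.
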